12.2 In what format will the research data be collected?

Paper
 Electronic
 Other – (*see below*)

If "Other" please specify::

12.3 Do you plan to obtain data from individuals located in the European Economic Area (EEA)*?

Yes
 No

If "YES" the data you obtain may be subject to the E.U. General Data Protection Regulation (GDPR). Click [here](#) for more information.

** The EEA includes the 28 states of the European Union and four additional countries: Iceland, Liechtenstein, Norway, and Switzerland. Note that this regulation may also apply to data obtained over the internet.*

12.4 Will data collected from individuals located in the EEA include any of the following? (mark all that apply)

Information about a Subject's Health
 Racial or Ethnic Origin
 Political Opinions
 Religious or Philosophical Beliefs
 Trade Union Membership

- Sexual Orientation
- Data concerning a person's sex life
- Biometric Data
- Genetic Data
- None

12.09 Will the study require the use of Mobile Apps?

- Yes
- No

List the names of each Mobile App:

StriveWeekly

12.10 Will the study use a web-based survey tool?

- Yes
- No

List the names of each web-based tool:

<https://harvard.az1.qualtrics.com/>

12.11 Select any personal device that will collect study data:

- Laptop
- Tablet & Smartphone
- None

12.12 Will the study involve study subjects using wearable technology as part of the study?

- Yes
- No

List the names of the wearable technology:

12.13 Will the data be managed by Harvard researchers either remotely or housed at Harvard (e.g., physically or Harvard Cloud Storage)?

- Yes
- No

12.14 Describe the identifiability of the data when stored:

- Will be directly labeled with personal identifying information (identifiable)

- Will be labeled with a code that the research team can link to personal identifying information *This refers to when the research team is using a crosswalk document to link identifiable data to research data and each dataset is kept separately.*
- Will not be directly identifiable but there will be a code held by the data source that links to the identities (Coded) – *i.e., if receiving data from another site*
- Will not be labeled with any personal identifying information, nor with a code that the research team can link to personal identifying information (Anonymous or De-identified)
- Other – *(see below)*

If "Other" please specify:

12.15 In what format will the research data be stored?

- Paper
- Electronic
- Other – *(see below)*

If "Other" please specify:

12.16 How will the consent forms be collected and stored?

- Paper
- Electronic

12.17 Will subject contact information or other individually identifiable subject information be stored in the data set?

- No
- Yes

12.18 Explain where the research data will be stored while the study is active (e.g., personal laptop, thumb drive, departmental computer server, office file cabinet, etc.).

During the study, documentation of identifying information within consent forms and participant ID key will be stored on Harvard Qualtrics, which will be accessible only by the PI of this study. The Harvard Qualtrics site login requires HarvardKey dual authentication. The electronic consent forms will be stored separately from survey responses. The Harvard Qualtrics surveys will be configured to use an auto-generated participant ID, matched to email addresses in the separate ID key.

The StriveWeekly Platform User Database for the Harvard-hosted instance will be stored on a HUIT-managed AWS EC2 instance. HUIT will provide [name] with access to this database.

Once all data collection is complete, [name] (StriveWeekly owner) will download the StriveWeekly user database onto a personal work laptop (due to remote work set-up) while logged into Harvard's network via Cisco VPN. At the same time, [name] in her role as the Harvard-affiliated study PI will download all the survey datasets from Qualtrics. Once all these datasets are downloaded as Excel files, email addresses in the StriveWeekly user database will be used to link all assigned participant IDs per the Qualtrics ID key. The datasets (platform database and Qualtrics surveys) will then all be merged into a password-protected master dataset using these participant IDs. This master file will thus have no identifying data within it. The password for the master data will be known only by the PI, and anyone listed in the IRB for the corresponding study (currently or in the

future). All downloaded files will be permanently deleted from the laptop, and the master dataset will be saved within the PI's Harvard O365 OneDrive. [name] (Graduate Assistant) and [name] (Graduate Assistant) will help with management of the resulting dataset.

12.19 What will happen to the data at the conclusion of the study? (check all that apply)

- Direct identifiers* and/or the key to the codes will be destroyed upon completion of the research (all data will be stripped of identifying information and/or the key to codes destroyed, identifiable paper documents shredded, identifiable electronic files purged, Identifiable electronic media securely erased).
- Retained for study record keeping purposes per institutional policy.
- Retained by the investigator for future research use.
- Retained for future research use (create repository/bank).
- Restricted use data will be destroyed or will be returned to the source.
- No direct or indirect identifiers* are being collected. This anonymous data will be retained at the discretion of the investigator.
- This research is a clinical trial conducted under FDA regulations. Direct identifiers* and/or the key to the codes will be destroyed as directed by the sponsor (IND/IDE holder) in accordance with FDA regulations.
- Other – *(see below)*

If "Other" please specify:..

Direct identifiers will still be stored on the Harvard Qualtrics. A copy of the Qualtrics ID key will be stored on the PI's Harvard OneDrive, password-protected by a password known by no one else. When the PI's affiliation with Harvard is terminated (June 2024), the PI will lose access to all of these direct identifiers.

Before PI loses access to these services, [name] will download a password-protected version of the master dataset that includes no direct identifiers. This version will include participants' responses to all study questions and their merge StriveWeekly platform data, including open-ended responses. See 13.2 for more information on sharing of de-identified datasets. The PI has already consulted with the Dean of Students Office, and received permission to retain de-identified copies of research datasets.

*** Direct identifiers.** *These are variables that point explicitly to particular individuals or units. Examples include: names, addresses, including ZIP and other postal codes, telephone numbers, including area codes, Social Security numbers, other linkable numbers such as driver's license numbers, certification numbers, etc.*

Indirect identifiers. *These are variables that can be problematic as they may be used together or in conjunction with other information to identify individual respondents. Examples include: detailed geographic information (e.g., state, county, province, or census tract of residence), organizations to which the respondent belongs, educational institutions (from which the respondent graduated and year of graduation), detailed occupational titles, place where respondent grew up, exact dates of events (birth, death, marriage, divorce), detailed income, offices or posts held by respondent.*

DATA TRANSFER

12.20 Do you anticipate that the research data will be transferred or transported from your possession to another at any time?

- Yes
- No *(skip to question #12.22)*

12.21 Explain what methods you will use to transfer/transport the data and how you will minimize the risks of a data breach during the transmission process.

[name] will be provided access to the Qualtrics data collection during the study, as well as access to payment tracking files in Harvard OneDrive. This folder will be shared to [name]'s email address, and the share settings will not allow anyone else to access the files. Once the study is over, [name] will have access to any identifiable data revoked.

[name] will be provided de-identified data files after the study is complete. This transfer will be coordinated by the study PI. Two types of data will be provided:

1. A subsample of the data derived from students endorsing identification with the LGBTQ+ community for secondary data analyses.

2. Transcripts of individual interviews for qualitative data analysis procedures.

This de-identified data files will be placed into a folder on the PI's Harvard OneDrive. This folder will be shared to [name]'s LLU email address, and the share settings will not allow anyone else to access the files. Once [name] has confirmed that all de-identified files are downloaded on their end, the folder will be deleted from OneDrive.

12.22 Will data be transferred from the EEA* to Harvard or another non-EEA location?

Yes

No

** The EEA includes the 28 states of the European Union and four additional countries: Iceland, Liechtenstein, Norway and Switzerland.*

DATA CONTROLS

12.23 Will (or has) a Certificate of Confidentiality (CoC) be (been) obtained for this study? If your study meets the definition of a clinical trial according to the NIH, a CoC will be automatically issued with your funding.

Yes

No

12.24 Does your protocol have a Data Use Agreement?

Yes

No

13. SHARING DATA WITH OTHERS

13.1 Will the data be released to anyone who is not on the Harvard University Area research team?

Yes

No (*skip to question #13.4*)

13.2 Other than the Harvard University Area research team, who will have access to the data?

Colleagues/Collaborators at other institutions

Transcribers/coders hired by the research team

Sponsor/Funding Agency

OpenScience or other framework (Specify: <https://osf.io/8dvjq/>)

Other (*see below*)

If "Other" please specify:

Collaborators at other institutions: While the data is being collected, [name] will be helping collect and process data via Harvard Qualtrics, the StriveWeekly platform, Harvard OneDrive, and Harvard Zoom. After the data collection is complete, [name]'s access to these services will be revoked. At that time [name] will then be provided de-identified data files. See details in 12.21 above.

OpenScience: a de-identified copy of main study variables (e.g., condition assignment, outcome measure total scores) will be uploaded to the PI's OSF profile. This copy of the dataset will contain none of the qualitative open-ended response data. In future published manuscripts, the PI will offer de-identified versions of other variables should other researchers wish to verify study results, or use study data for secondary analysis or meta-analysis research.

Other: See 5.25 and 12.18 for explanation of [name]'s external role as StriveWeekly website owner

13.3 How will the data be shared/disclosed beyond the Harvard University Area research team?

- Without any identifiers
- Coded
- With Identifiers

13.4 Will you be sharing research findings with study participants?

- Yes (see below)
- No

If "Yes" please describe which findings will be shared, when they will be shared, and how they will be shared with participants (in-person, over the telephone, etc.):

13.5 Does the study include establishing a repository for sharing data or specimens with other researchers?

- Yes (If so, please know that a separate IRB submission will be needed if a data or specimen repository will be created)
- No

GENOMIC DATA SHARING

13.6 Will you be submitting data to a national data repository (dbGaP, GEO, etc.) or other type of repository for broad sharing of data?

- Yes
- No

13.7 Will you require a Genomic Data Sharing (GDS) Institutional Certification per NIH GDS policy?

- Yes
- No

13.8 Include a description of all fields to be submitted to the repository:

13.9 Describe the plan for de-identifying data for inclusion in the repository, including how the key linking the identity of participants will be maintained and who will have access:

If data will be prospectively collected, specific elements are required to be included in the informed consent form that you will be using in this study. Please see the [NIH guidance document](#).

If data that will be submitted have already been collected under another IRB or other collection protocol, please be sure to attach a copy of the IRB approval and approved consent form(s) used to collect the underlying data/specimens to the “Local Site Documents” section in the ESTR SmartForm.

Study title: Randomized Controlled Trial (RCT) of StriveWeekly for Anxiety and Depression Prevention for College Students During COVID-19

NCT #:NCT04927845

Document date: 06/01/2023

The following “Data analysis” section is an excerpt from a proposal titled “Randomized Controlled Trial of StriveWeekly during COVID-19” that was submitted on 08/14/2020 to Harvard University Foundations of Human Behavior Initiative Proposal.

Data analysis. For assessing intervention effects, piecewise LME models will be run in predicting change in outcome scores. Included variables of group, time, group by time interaction, and covariates will be treated as fixed effects, whereas participant intercepts and outcome slopes will be allowed to vary randomly. Between-group and with-group effect sizes (d) will be calculated based on estimated marginal means. Moderator and mediator analyses will be selected *post hoc*, based on data completeness. Given the number of exploratory analyses that will be conducted, all significant findings will be tested against Benjamini-Hochberg critical values, on order to control for false discovery rate (i.e., Type I error).

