4. RESEARCH PURPOSE

4.1 Provide a brief, non-technical description of the purpose of the research, including the research questions that you hope to answer.

We aim to evaluate the effectiveness of StriveWeekly in preventing symptoms of anxiety and depression within a remote campus learning environment. The use of a waitlist condition will allow us to experimentally assess if the online intervention is responsible for decreasing / preventing worsened anxiety, depression, and stress symptoms over time. Given the previously established effectiveness of StriveWeekly as a universal prevention program, we expect students in the intervention condition to experience significantly better symptoms compared to the waitlist from baseline to posttest.

Alternatively, if the remote campus learning environment and/or the broad pandemic context interferes with the acceptability or effectiveness of StriveWeekly, then we would expect to see no significant differences between the online intervention condition and waitlist condition from baseline to posttest. The results of this project are intended to contribute to generalizable, and publishable knowledge in the field.

Secondary aims include: (a) testing moderators of intervention effectiveness and (b) evaluating the intervention in terms of acceptability (e.g., feedback on program name; demographically representativeness of student user sample; satisfactory adherence and satisfaction rates). Exploratory moderation analyses across groups will help determine whether or not the intervention condition produces unique or additive effects for students with certain characteristics over and above changes demonstrated by similar students in the waitlist condition. Acceptability analyses will allow for more nuanced evaluation of StriveWeekly's effectiveness as a program, beyond its ability to facilitate symptom reduction. Secondary analyses and follow up interviews with diverse subsamples of students will help to assess generalizability of StriveWeekly outcomes, determine acceptability among underserved populations, and inform future research.

4.2 Describe the scientific background, rationale for the study, and importance of this research in adding to existing knowledge.

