With the COVID-19 pandemic completely altering the landscape of higher education, students are experiencing more stress than ever. While there has been a full return to in-person instruction for the 2021-2022 academic year, students are still navigating travel restrictions, isolation protocols, and social distancing. Thus, offering an online mental health program such as StriveWeekly will provide students with stress management support regardless of where they are. However, the online intervention's effectiveness has not been tested in the midst of a pandemic or after a remote learning setting. Additionally, the extant literature is limited in the ability to determine to what extent adaptations to therapeutic tools are needed to meet the psychological needs of Sexual and Gender Minority (SGM) individuals. Therefore, in addition to offering StriveWeekly as a service to students, a research trial will be conducted to evaluate the program's effectiveness in addressing anxiety and depression symptoms within this broader unprecedented context. Targeted analyses and follow-up interviews conducted with historically underserved sexual and gender minority students will additionally help support generalizability of StriveWeekly. The results of this trial will support evidence of the effectiveness of offering such online mental health interventions to university students, even when a campus is experiencing unique stressors.

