Data collection. Prior to beginning any research procedures, students will provide their informed consent online via Qualtrics. Participants will be required to login to Qualtrics via HarvardKey Shibboleth, which will be configured to only allow currently active Harvard accounts. Once consent has been obtained for an individual student, they will be directed to an online survey for the study **baseline assessment**. The baseline survey will be open for two weeks. Students assigned to the intervention group will receive an access code in the email, allowing them to access the online platform and set-up their account. The intervention group will then be active for seven weeks, after which the **posttest survey** will open to the intervention group and waitlist group for one-two weeks. There will then be a pause in study activity and data collection from mid-November through winter break. Thereafter, there will be a **2-month follow-up survey** and students who were assigned to the waitlist group will gain access to the online intervention for seven weeks. After this delayed access group completes the intervention, there will be a **5-month follow-up survey** for all participants from both conditions. After the fourth survey, subsets of participants may be invited to additional compensated opportunities to provide further feedback as research data. See timeline table below.

Activity	Timeline
Promotion	August 16 – Sept 6
Recruitment + Baseline Survey	Sept 7 – Sept 17
First Intervention Round	Sept 20 – Nov 7
•Weekly goal-setting & Time management	Sept 20 - 26
•Unhelpful thinking habits	Sept 27 - Oct 3
•Quality time on values & fun	Oct 4 - Oct 10
•Relaxation strategies & Mindfulness	Oct 11 - Oct 17
•Sleep hygiene	Oct 18 - Oct 24
•Physical exercise	Oct 25 - Oct 31

•Wrap-up	Nov 1 - Nov 7
Posttest Survey	Nov 8 – Nov 19
Break	
2-month Follow-up Survey	Jan 24 - Feb 4
Second Intervention Round	Feb 7 – Apr 3
•Weekly goal-setting & Time management	Feb 7 - Feb 13
•Unhelpful thinking habits	Feb 14 - Feb 20
•Quality time on values & fun	Feb 21 - Feb 27
•Relaxation strategies & Mindfulness	Feb 28 - Mar 6
•Sleep hygiene	Mar 7 - Mar 13
Spring break	Mar 14 – Mar 20
•Physical exercise	Mar 21 - Mar 27
•Wrap-up	Mar 28 - Apr 3
5-month Follow-up Survey	Apr 4 - 15
Additional feedback from subgroups TBD	April - May 2022

Conditions

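### Does leaving the surveys and knots of the piecewise model unstated put the baseline-to-posttest comparison at risk?

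*SAP*

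**What the plan says.** The SAP, Data analysis, is one paragraph taken from a proposal "submitted on 08/14/2020". The SAP document itself is dated 06/01/2023. The paragraph states that "piecewise LME models will be run in predicting change in outcome scores", that "Included variables of group, time, group by time interaction, and covariates will be treated as fixed effects", and that participant intercepts and slopes are random. Between-group and within-group "effect sizes (d) will be calculated based on estimated marginal means". It gives no list of surveys, no knots, no coding of time and no survey at which d is read.

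Protocol section 4.1 supplies the contrast: the investigators expect "students in the intervention condition to experience significantly better symptoms compared to the waitlist from baseline to posttest". Section 4.2 refers to the "full return to in-person instruction for the 2021-2022 academic year", which places the timetable in section 5.1 in that year:

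- baseline survey from Sept 7;
- first intervention round Sept 20 to Nov 7;
- posttest survey from Nov 8;
- 2-month survey from Jan 24;
- second round Feb 7 to Apr 3, in which "students who were assigned to the waitlist group will gain access to the online intervention for seven weeks";
- 5-month survey from Apr 4, "for all participants from both conditions".

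**The concern.** A piecewise model is defined by its pieces, and these are not given. A common two-piece layout is a treatment phase followed by a follow-up phase, with the knot at posttest. Here the follow-up phase is not uniform for the waitlist: it contains an untreated winter interval and then that arm's own treatment. One straight line through both cannot fit, and because d is taken from fitted means, the misfit would pass into the reported effects.

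The hypothesised posttest difference would then depend partly on how the waitlist responded months later. The 2-month difference, which on the timetable is the last comparison before the waitlist's round, would be understated. Knots chosen after the data are seen could also move the headline estimate.

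**Working it through.** The plan has no figure of its own to reproduce, so the check is on what each way of completing the model would estimate.

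**Inputs.** Survey opening days counted from Sept 7 are 0, 62, 139 and 209 (Protocol 5.1). The illustrative difference is 0.25 SD in favour of the intervention, the d of the prior trial (Protocol 4.2). Three things are assumed: the between-group difference persists to the 2-month survey, waitlist catch-up by 5 months is none, half or full, and data are complete. Write d1, d2, d3 for the true differences at posttest, 2 months and 5 months, with zero at baseline.

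**Four surveys, one knot at posttest.** The line has three mean parameters per arm for four surveys, so one contrast is left unfitted:

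L = d2 − (70/147)·d1 − (77/147)·d3 = d2 − 0.476·d1 − 0.524·d3

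This is the distance of the 2-month difference from the straight line joining posttest to 5 months. Its squared coefficients sum to 0.227 + 1 + 0.274 = 1.501. Hence:

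- fitted posttest = d1 + (0.476/1.501)·L = d1 + 0.317·L
- fitted 2-month = d2 − (1/1.501)·L = d2 − 0.666·L

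Independence, a random intercept, and a random intercept plus slope all give these same values.

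| True d1, d2, d3 | L | Fitted posttest | Fitted 2-month |
|---|---|---|---|
| 0.25, 0.25, 0 (full catch-up) | 0.131 | 0.292 | 0.163 |
| 0.25, 0.25, 0.125 (half) | 0.065 | 0.271 | 0.206 |
| 0.25, 0.25, 0.25 (none) | 0 | 0.250 | 0.250 |
| 0.25, 0.12, 0 (steady fade) | 0.001 | 0.250 | 0.119 |
| 0, 0, 0 (no effect in either round) | 0 | 0 | 0 |

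**Sensitivity, full catch-up.** With assumed retention of 75/60/50% at the three later surveys, the posttest value is 0.282 and the 2-month value 0.163. If the working covariance is AR(1) by survey with correlation 0.7, the changes from baseline are 0.254 and 0.128. Serial correlation therefore shrinks the posttest shift to 0.004 and raises the 2-month shift to 0.250 − 0.128 = 0.122.

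**Other completions, same truth (0.25, 0.25, 0).** Knots at posttest and at the 2-month survey give 0.250, 0.250 and 0, exactly. The first three surveys with one knot at posttest give 0.250 and 0.250, exactly.

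**Scale.** Protocol 7.1 gives no sample size. Section 11.2 expects 40 raffle winners at odds of 1:10 to 1:25, which implies about 40 × 10 = 400 to 40 × 25 = 1,000 participants, or 200 to 500 per arm if the arms are equal. With an assumed between-survey correlation r, the SE of a difference in change is √(4(1 − r)/n). This is 0.100 for n = 200, r = 0.5, and 0.049 for n = 500, r = 0.7. The largest posttest shift, 0.042, is 0.4 to 0.9 SE before any allowance for the 18 randomised residential units. The corresponding 2-month shift, 0.087, is 0.9 to 1.8 SE.

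**The case for a change.** The strongest case for a change is that the choice is open and the answers differ. A single knot placed at the 2-month survey on all four surveys would give a fitted posttest difference of 0.158 in the full catch-up example, so completions can move the headline either way. Stating the knots costs a few sentences, and it is reasonable to want the main contrast unaffected by later waitlist behaviour. The omission and the arithmetic both stand.

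The step from omission to bias does not. Piecewise models are used to break time where the phase changes. The timetable shows two changes after baseline: the first round ends just before the posttest survey, and the waitlist's round begins just after the 2-month survey. Knots there give one piece per interval. That is the same mean model as categorical time over four surveys, so rewriting the SAP in those terms gains nothing in what is estimated. A lone knot at 2 months ignores the end of the first round, and in the example it also fits a difference of 0.051 at baseline where the true one is zero, a visible sign of misfit.

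The random effects need ordinary judgement. An intercept and three correlated slopes need 10 variances and covariances plus a residual variance, 11 parameters against the 10 elements of a four-survey covariance matrix. An analyst would keep an intercept and one slope.

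Two supports for the concern are weaker than they look. The 2020 proposal date adds little, since the text was put forward as this trial's SAP in 2023, after the timetable had run. Protocol 4.2 reports that symptom improvements lasted to 3 months in the prior trial. It does not say that the difference between arms did, and the 0.292 and 0.163 figures require that.

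One loose end remains outside the model. The waitlist paragraph of Protocol 5.1 ties access to completing the posttest survey, whereas the timetable starts it after the 2-month survey. The two statements must be reconciled before the 2-month comparison is described as untreated. The posttest comparison is unaffected.

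**Conclusion.** The SAP leaves out the surveys, the knots and the time point for d, but nothing it does state produces a wrong result. The distortion arises only if an analyst fits all four surveys with one follow-up slope across the waitlist's treatment. Even then the posttest shift is between 0 and about 0.04 SD, assuming a 0.25 SD difference held to 2 months and catch-up between none and full. The 2-month shift could reach 0.087 SD under the random-effects structure the SAP names, or about 0.12 SD under strong serial correlation, but the documents do not name that comparison as a hypothesis. When neither round has an effect the shift is zero, so no false positive arises from it. Protocol 4.1 fixes the contrast of interest and section 5.1 shows where the phases change. Together they lead a competent analyst to a model that returns the posttest difference exactly. No change to the plan is needed.
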